## **15. DIRECT ACCESS TO SOURCE DATA/DOCUMENTS**

### **15.1. Study Monitoring**

Before an investigational site can enter a subject into the study, a representative of Viela Bio, Inc. or of the CRO will visit the investigational study site to:

- Determine the adequacy of the facilities.
- Discuss with the investigator(s) and other personnel their responsibilities with regard to protocol adherence, and the responsibilities of Viela Bio, Inc. or its representatives. This will be documented in a Clinical Study Agreement between Viela Bio, Inc. and the investigator.

During the study, a monitor from Viela Bio, Inc. or representative will have regular contacts with the investigational site, for the following:

- Provide information and support to the investigator(s).
- Confirm that facilities remain acceptable.
- Confirm compliance with the principles of GCP and regulatory requirements.
- Review of written informed consent forms for subjects screened/enrolled
- Confirm that the investigational team is adhering to the protocol, that data are being accurately recorded in the eCRFs, and that investigational product accountability checks are being performed.
- Perform source data verification. This includes a comparison of the data in the case report forms with the subject's medical records at the hospital or practice, and other records relevant to the study for accuracy and completeness. This will require direct access to all original medical and other trial related records for each subject (e.g. clinic charts).
- Record and report any protocol deviations not previously sent to Viela Bio, Inc.
- Confirm AEs and SAEs have been properly documented on eCRFs and confirm any SAEs have been forwarded to Viela Bio, Inc. or representative and those SAEs that met criteria for reporting have been forwarded to the IRB.

During scheduled monitoring visits, the Investigator and the investigational site staff must be available to meet with the study monitor in order to discuss the progress of the study, make necessary corrections to CRF entries, respond to data clarification requests and respond to any other study-related inquiries of the monitor.

The monitor will be available between visits if the investigator(s) or other staff needs information or advice.

### **15.2. Audits and Inspections**

Authorized representatives of Viela Bio, Inc., a regulatory authority, an IEC or an IRB may visit the site to perform audits or inspections, including source data verification. The purpose of a Viela Bio, Inc. audit or inspection is to systematically and independently examine all study-

related activities and documents to determine whether these activities were conducted, and data were recorded, analyzed, and accurately reported according to the protocol, GCP guidelines of the International Council for Harmonization (ICH), and any applicable regulatory requirements.

Initial IRB approval, and all materials approved by the IRB for this study including the patient consent form and recruitment materials must be maintained by the Investigator and made available for inspection.

In addition to the above, representatives of Viela Bio, Inc.'s auditing staff or government inspectors may review the conduct/results of the study at the investigational site.

The investigator should contact Viela Bio, Inc. immediately if contacted by a regulatory agency about an inspection. The Investigator cooperates with the auditor(s), makes available to the auditor all requested documentation, and ensures that issues detected during the course of these audits are satisfactorily resolved. The Investigator supplies Viela Bio, Inc. with copies of all documentation and correspondence related to regulatory agency audits as outlined in the Clinical Trial Agreement. If the results of the audit result in a Form FDA-483 (or similar document from another regulatory agency), the Investigator promptly provides a copy to a Viela Bio, Inc. representative and a draft response to Viela Bio, Inc. prior to submission to the regulatory agency.

## **16. QUALITY CONTROL AND QUALITY ASSURANCE**

To ensure compliance with GCP and all applicable regulatory requirements, Viela Bio, Inc. may conduct a quality assurance audit. Please see Section [15.2](#) for more details regarding the audit process.

## **17. ETHICS**

### **17.1. Ethics Review**

The final study protocol, including the final version of the ICF, must be approved or given a favorable opinion in writing by an IRB or IEC as appropriate. The investigator must submit written approval to Viela Bio, Inc. or representative before he or she can enroll any patient into the study.

The PI is responsible for informing the IRB or IEC of any amendment to the protocol in accordance with local requirements. In addition, the IRB or IEC must approve all advertising used to recruit subjects for the study. The protocol must be re-approved by the IRB or IEC upon receipt of amendments and annually, as local regulations require.

The PI is also responsible to adhere to requirements stipulated by the respective IRB/IEC and for providing the IRB/IEC with reports of any reportable serious adverse drug reactions from any other study conducted with the investigational product. Viela Bio, Inc. will provide this information to the PI.

Progress reports and notifications of serious adverse drug reactions will be provided to the IRB or IEC according to local regulations and guidelines.

Copies of all correspondence between the Investigator and the IRB/IEC is provided to Viela Bio, Inc.'s representative.

## **17.2. Ethical Conduct of the Study**

The study will be performed in accordance with ethical principles that have their origin in the Declaration of Helsinki and are consistent with ICH/GCP, applicable regulatory requirements and the Viela Bio, Inc.'s policy on Bioethics.

## **17.3. Written Informed Consent**

The PI(s) and other members of the study site's treating team will ensure that the patient or legally authorized representative is given full and adequate oral and written information about the nature, purpose, possible risk and benefit of the study. Patients or legally authorized representative must also be notified that they are free to discontinue from the study at any time. Patients or legally authorized representative will be informed that their study record and medical records/documents that pertain directly to the study will be reviewed and possibly copied by Viela Bio, Inc. or its designee, or a governmental agency (such as the FDA), and that every effort will be made to maintain patient confidentiality. The patient or legally authorized representative should be given the opportunity to ask questions and allowed time to consider the information provided.

The Informed Consent must be witnessed and dated by the Investigator or his/her designee, and the original retained by the Investigator/Study Site as part of the patient's study record.

The patient's or legally authorized representative's signed and dated informed consent must be obtained before conducting any study procedures.

The PI(s) must maintain the original, signed ICF. A copy of the signed ICF must be given to the patient or legally authorized representative.

Subjects may be re-screened within 30 days under the current and signed ICF.

The informed consent document must be fully approved by an institutional review board (IRB) or an independent ethics committee (IEC) prior to its use with study participants.

## **18. DATA HANDLING AND RECORD KEEPING**

### **18.1. Inspection of Records**

Viela Bio, Inc. will be allowed to conduct site visits to the investigation facilities for the purpose of monitoring any aspect of the study. The Investigator agrees to allow the monitor to inspect the drug storage area, study drug stocks, drug accountability records, subject charts and study source documents, and other records relative to study conduct.

**18.2. Retention of Records**

The PI must maintain all documentation relating to the study for a period of 2 years after the last marketing application approval, or if not approved 2 years following the discontinuance of the test article for investigation. If it becomes necessary for Viela Bio, Inc. or the Regulatory Authority to review any documentation relating to the study, the Investigator must permit access to such records.

**19. PUBLICATION POLICY**

Publication of study data is addressed in the Clinical Trial Agreement between Viela Bio, Inc. and Investigator(s) and/or Institution(s).

## **APPENDIX 2. NATIONAL INSTITUTE OF ALLERGY AND INFECTIOUS DISEASE (NIAID) AND FOOD AND ALLERGY ANAPHYLAXIS NETWORK (FAAN) GUIDANCE FOR ANAPHYLAXIS DIAGNOSIS**

NIAID and FAAN define anaphylaxis as a serious allergic reaction that is rapid in onset and may cause death (Sampson, Munoz-Furlong et al. 2006). They recognize 3 categories of anaphylaxis, with criteria designated to capture from 80% of cases (category 1) to >95% of all cases of anaphylaxis (for all 3 categories).

1. Acute onset of an illness (minutes to several hours) with involvement of the skin, mucosal tissue, or both (e.g., generalized hives, pruritus or flushing, swollen lips-tongue-uvula) AND AT LEAST ONE OF THE FOLLOWING
  - a. Respiratory compromise (e.g., dyspnea, wheeze-bronchospasm, stridor, reduced PEF, hypoxemia)
  - b. Reduced BP or associated symptoms of end-organ dysfunction (e.g., hypotonia [collapse], syncope, incontinence)
2. Two or more of the following that occur rapidly after exposure to a likely allergen for that patient (minutes to several hours):
  - a. Involvement of the skin-mucosal tissue (e.g., generalized hives, itch-flush, swollen lips-tongue-uvula)
  - b. Respiratory compromise (e.g., dyspnea, wheeze-bronchospasm, stridor, reduced PEF, hypoxemia)
  - c. Reduced BP or associated symptoms (e.g., hypotonia [collapse], syncope, incontinence)
  - d. Persistent gastrointestinal symptoms (e.g., crampy abdominal pain, vomiting)
3. Reduced BP after exposure to known allergen for that patient (minutes to several hours):
  - a. Infants and children: low systolic BP (age specific) or greater than 30% decrease in systolic BP
  - b. Adults: systolic BP of less than 90 mm Hg or greater than 30% decrease from that person's baseline

### APPENDIX 3. AN APPROACH TO MANAGEMENT OF ANAPHYLACTIC AND HYPERSENSITIVITY REACTIONS

Severity of Symptoms	Treatment

Mild
 
Mild reactions such as headache, nausea, nonpruritic rash, or mild hypersensitivity reactions including localized cutaneous reactions such as mild pruritus, flushing, rash, dizziness, headache, <math>\leq 20</math> mmHg change in systolic BP from pre-infusion measurement
	
Evaluate subject, including close monitoring of vital signs. At the discretion of the investigator, treat subject, for example, with:
 
 
• Normal saline (~500-1000 mL/hour IV) and/or
 
• Diphenhydramine 50 mg IV or equivalent and/or
 
• Acetaminophen 500-650 mg or equivalent dose of paracetamol and/or
 
• Topical antihistamines and/or low-potency topical corticosteroid preparations and/or
 
• Anti-nausea medication, as needed
 

Moderate
 
Reactions which may include generalized rash or urticaria, palpitations, chest discomfort, shortness of breath, hypo- or hypertension with <math>> 20</math> mmHg change in systolic BP from pre-infusion measurement
	
Evaluate subject, including close monitoring of vital signs. Treat subject, for example, with:
 
 
• Normal saline (~500-1000 mL/hour IV) and/or
 
• Diphenhydramine 50 mg IV or equivalent and/or
 
• Acetaminophen 500-650 mg or equivalent dose of paracetamol and/or
 
• IV corticosteroids, such as hydrocortisone 100 mg or methylprednisolone 20-40 mg
 

Severe
 
Above plus fever with rigors, hypo- or hypertension with <math>\geq 40</math> mmHg change in systolic BP from pre-infusion measurement, signs of end organ dysfunction (e.g., symptomatic hypotension such as pre-syncope, syncope, seizure), or wheezing, angioedema, or stridor
	
Evaluate subject, including close monitoring of vital signs. Treat subject, for example, with:
 
 
• Normal saline (~500-1000 mL/hour IV) and/or
 
• Diphenhydramine 50 mg IV or equivalent and/or
 
• Acetaminophen 500-650 mg or equivalent dose of paracetamol and/or
 
• IV corticosteroids, such as hydrocortisone 100 mg or methylprednisolone 20-40 mg
 
 
Call emergency medical transport for transport to emergency hospital based on judgment of the investigator


Life threatening
 
Defined as a reaction that is life threatening and requires pressor and/or ventilator support or shock associated with acidemia and impairing vital organ function due to tissue hypoperfusion
	
Evaluate subject, including close monitoring of vital signs. Maintain airway, oxygen if available. Treat subject immediately, for example with:
 
 
• Normal saline (~500-1000 mL/hour IV)
 
• Epinephrine for bronchospasm, hypotension unresponsive to IV fluids, or angioedema. Dose and route as per local standard of care, example, epinephrine 1:1000, 0.5-1.0 mL administered SC for mild cases and intramuscular for more severe cases
 
• IV corticosteroids, such as hydrocortisone 100 mg or methylprednisolone 20-40 mg
 
• Diphenhydramine 50 mg IV or equivalent
 
• Acetaminophen 500-650 mg or equivalent dose of paracetamol
 
 
Call emergency medical transport for transport to emergency hospital based on judgment of the investigator

BP = blood pressure; IV = intravenous; SC = subcutaneous

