Subjects with evidence of renal allograft dysfunction (rising serum creatinine not attributable to technical complications) and/or evidence of cell-mediated or antibody mediated rejection on biopsy will be treated with additional immunosuppression, as clinically indicated and according to standard care at each participating clinical site. Whether to continue VIB4920+belatacept will be determined based on the histologic grade of the rejection and the clinical response to immunosuppressive therapy, as defined below.

Written informed consent and any locally required authorization (e.g., data privacy) will be obtained from the subject prior to performing any protocol-related procedures, including screening evaluations. Patients may be screened between Day -28 and Day -1 prior to transplantation, with eligibility reconfirmed on Day 0 prior to induction of anesthesia for transplant surgery and prior to administration of Thymoglobulin or methylprednisolone. Subjects will be admitted to the transplant center for administration of VIB4920 and belatacept, observation and assessment of safety/tolerability and may be discharged after administration of belatacept+VIB4920 on Day 3 or 4 (at the discretion of the investigator) following completion of all scheduled Visit 4 assessments. Subjects will return to the study center for safety monitoring on Day 7 and for administration of study medication(s) and safety monitoring on Week 2; then every 2 weeks for 5 visits (at the end of Weeks 4, 6, 8, 10 and 12), and then monthly for 9 visits (at the end of Weeks 16, 20, 24, 28, 32, 36, 40, 44 and 48). All subjects will be followed on study through Week 48 for acute rejection, graft survival and patient survival. Subjects who prematurely discontinue treatment with VIB4920 and/or belatacept will undergo an End-of-Treatment visit at time of discontinuation and follow Schedule of Assessments through Week 48 and at least three months after last dose with VIB4920 and/or belatacept completing the study with End of Study visit. Subjects who are unwilling to comply with study schedule after early discontinuation of treatment should undergo End-of-Treatment/End-of-Study visit at time of discontinuation and undergo complete safety follow up at 4, 8, and 12-weeks after end treatment visit. Subjects who wish to prematurely discontinue study participation should be asked to undergo an End-of-Study visit assessment before withdrawing consent.

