#### **10.1.4.2. Intravenous administration**

An experienced and qualified staff member will place the IV access.

VIB4920 will be infused using an IV infusion pump. Each subject must receive the entire volume of investigational product solution in the IV bag over at least 90 minutes (approximately 2.8 mL/min). Investigational product must be infused through a low-protein binding 0.2- or 0.22- $\mu$ m in-line filter. Vital signs will be obtained prior to the start of each VIB4920 infusion.

A physician must be present at the site or immediately available to respond to emergencies during administration of investigational product. Fully functional resuscitation facilities should be available.

Further information on VIB4920 preparation and administration is provided in the IP Manual.

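### Appendix 3 lists epinephrine only for life-threatening reactions, although two of the signs it is printed for, angioedema and bronchospasm (wheezing), belong to the Severe row

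*Protocol*

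**What the plan says.** Protocol Appendix 3 sorts anaphylactic and hypersensitivity reactions into Mild, Moderate, Severe and Life-threatening, and gives example treatments for each.

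- **Severe, signs.** Besides rigors and a systolic change of at least 40 mmHg, the row includes "signs of end organ dysfunction (e.g., symptomatic hypotension such as pre-syncope, syncope, seizure), or wheezing, angioedema, or stridor".
- **Severe, treatment.** The row lists saline, diphenhydramine, acetaminophen and IV corticosteroids, then: "Call emergency medical transport for transport to emergency hospital based on judgment of the investigator".
- **Life-threatening, definition.** "Defined as a reaction that is life threatening and requires pressor and/or ventilator support or shock associated with acidemia", with impaired vital organ function.
- **Life-threatening, treatment.** The same four drugs and the transport sentence, plus "Epinephrine for bronchospasm, hypotension unresponsive to IV fluids, or angioedema". Dose and route follow local standard of care. The example given is a 1:1000 solution, 0.5-1.0 mL, "administered SC for mild cases and intramuscular for more severe cases".

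Appendix 2, which sets out the criteria for anaphylaxis, gives as one criterion "Respiratory compromise (e.g., dyspnea, wheeze-bronchospasm, stridor, reduced PEF, hypoxemia".

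Section 10.1.4.2 adds a general safeguard: "A physician must be present at the site or immediately available to respond to emergencies during administration of investigational product". It also says that full resuscitation facilities should be available.

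**The concern.** A table tiered by severity is read by row. Site staff who see angioedema or wheezing during an infusion will go to the Severe row, because that is where those signs are printed. There they find the Moderate drugs and a transport instruction. The drug that the same table names for angioedema and bronchospasm is one row further down, behind a threshold of pressor support, ventilator support or shock.

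What is at stake is prompt treatment of a severe infusion reaction. The regimen combines several infused biologics, and Section 5.2.3 says that there is no clinical experience with dual costimulation blockade in humans. Emergency guidance should point to the drug that its own text indicates for the sign in front of the reader.

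**Working it through.** No statistical figure is involved. The check is a comparison of the table's rows, then a test case against Appendix 2.

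**Step 1. Drug entries by row (Appendix 3).**

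| Row | Drug entries | Epinephrine | Transport |
|---|---|---|---|
| Mild | saline, diphenhydramine, acetaminophen, topical agents, anti-nausea medication | no | no |
| Moderate | saline, diphenhydramine, acetaminophen, IV corticosteroids (4) | no | no |
| Severe | the same 4 at the same doses | no | yes |
| Life-threatening | the same 4 plus epinephrine (5) | yes | yes |

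Severe minus Moderate: 4 - 4 = 0 drugs added. Life-threatening minus Severe: 5 - 4 = 1 drug added, epinephrine. It appears in 1 row of 4 and nowhere else in the protocol or SAP.

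**Step 2. Printed epinephrine indications against Severe-row signs.**

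- Angioedema: a Severe sign, in the same word.
- Bronchospasm: a Severe sign in the form of wheezing. The link is Appendix 2, which pairs wheeze and bronchospasm as one example of respiratory compromise.
- Hypotension unresponsive to IV fluids: not counted. Giving saline in the Severe row and moving non-responders to the row defined by pressor need is a coherent sequence.

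So 2 of 3 printed indications are Severe-row signs.

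**Step 3. Can the protocol's own anaphylaxis definition land in the Severe row?** Category 1 in Appendix 2 needs acute skin or mucosal involvement plus either respiratory compromise or reduced blood pressure with its associated symptoms. Take acute generalized urticaria with wheezing, without shock and without need for a pressor or ventilator.

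- Appendix 2: skin involvement (hives) plus respiratory compromise (wheeze) meets category 1.
- Appendix 3: generalized urticaria is a Moderate sign, and the Severe row is the Moderate signs plus, among others, wheezing. The case is Severe. It does not reach the Life-threatening definition.
- Result: a reaction that meets the anaphylaxis criteria is assigned to a row that does not list epinephrine.

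**Step 4. Wording of the epinephrine entry.** It gives a subcutaneous route for mild cases, inside a row restricted to life-threatening reactions. That phrase has no sensible application there.

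**The case against.** The strongest reply is that the table is a graded scheme. A sign can occur at two levels of severity, with treatment escalating between them: bronchospasm and angioedema in the bottom row would then mean bronchospasm and angioedema severe enough to need pressor or ventilator support. The wheezing limb also depends on a diagnostic appendix, so only angioedema is a same-word match.

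The last remark is fair. The graded reading does not remove the problem. On that reading the table shows its own drug for angioedema or bronchospasm only once there is shock or a need for pressor or ventilator support, and the phrase about mild cases is left without meaning.

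The mitigating text does stand. The lists are introduced as examples. Dose and route are local. The physician and resuscitation provisions of Section 10.1.4.2 apply to every VIB4920 infusion. Section 13.2.1.3 cites Appendix 3 in the list of adverse events of special interest, not as a treatment order. Section 8.3 already makes anaphylaxis or a serious hypersensitivity reaction attributed to VIB4920 a reason to stop study drug.

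Two stronger readings are tempting and are not supported:

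- **That the protocol withholds epinephrine from severe reactions.** It does not. The row omits the drug, and nothing prevents the physician from giving it.
- **That the infusion schedule measures the harm.** Each subject has 17 planned VIB4920 infusions: Day 1, Day 3 or 4 and Weeks 2, 4, 6, 8 and 10 make 7, and every four weeks from Week 12 to Week 48 makes 10. If discharge precedes Week 2, 17 - 2 = 15 fall at return visits, which begin "for administration of study medication(s) and safety monitoring on Week 2" (Section 7.1). These counts describe exposure, not harm from this wording. Return visits take place at the study center under the same Section 10.1.4.2 provisions, so they do not imply weaker care. The documents give no reaction rate for this regimen, and Section 5.2.2 reports no infusion-related reactions in the two clinical studies of VIB4920 that preceded it.

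**Conclusion.** The point holds as a wording fault in safety guidance and should be corrected. The Severe drug list adds nothing to the Moderate list, two of the three printed epinephrine indications are Severe-row signs, and a reaction that meets Appendix 2's anaphylaxis criteria can be assigned to a row without epinephrine. The misplaced phrase on the subcutaneous route is a smaller fault in the same entry.

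The conclusion assumes that wheezing may be read as bronchospasm, as Appendix 2 pairs them; without that step the overlap is angioedema alone, and it still exists. It is limited to the text of this appendix: the IP Manual and the Safety Handling Plan, to which the protocol refers, were not available and may say more. Events may be few, and their number cannot be estimated from the documents. No endpoint, analysis set, estimate or decision rule is affected.

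**What to change.** Make two edits to the Appendix 3 table.

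1. **Severe row.** Add an entry: *Epinephrine for bronchospasm or angioedema; dose and route as per local standard of care.* The hypotension indication can stay in the Life-threatening row alone, since the saline-then-escalate sequence is coherent.
2. **Life-threatening row.** Delete only the words that give the subcutaneous route for mild cases. Keep the 1:1000 concentration, the 0.5-1.0 mL volume and the intramuscular route. They are the only epinephrine dose and route details printed in the protocol, so cutting the entry back to local standard of care would remove guidance from the most urgent row.

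The sponsor's clinicians should settle the final text. The cost is one wording change, carried in the next amendment and its IRB/IEC submission (Section 17.1) at approximately four sites. It adds no visits, patients or data fields.
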